Shire Pharmaceuticals also proposed to conduct a drug utilization study as part of their risk management plan to assess effectiveness of these measures: The study described in this protocol has been designed to evaluate drug utilization and to monitor inappropriate use of Intuniv[®] in Europe, Shire Pharmaceuticals considers this study an important activity to evaluate whether Intuniv[®] is being prescribed within the approved SmPC and whether current risk minimisation measures are adequate.

Shire Pharmaceuticals has launched/ plans to launch Intuniv[®] from January 2016 onwards in Belgium, Denmark, Finland, Germany, Ireland, Netherlands, Norway, Spain, Sweden, and UK for treatment of ADHD. Expected launch dates are given in Table 2. In order to evaluate drug utilization and to monitor appropriate and potential inappropriate use of Intuniv[®] in Europe, Shire Pharmaceuticals proposed to conduct a drug utilization study as part of their risk management plan.

The indication for Intuniv[®] given in the Summary of Product Characteristics is as follows (1):

Intuniv[®] is indicated for the treatment of attention deficit hyperactivity disorder (ADHD) in children and adolescents 6 to 17 years old for whom stimulants are not suitable, not tolerated or have been shown to be ineffective. Intuniv[®] must be used as a part of a comprehensive ADHD treatment program, typically including psychological, educational and social measures.

Based on this label, inappropriate use of Intuniv® may include use in

- Patients with indications other than ADHD
- Children less than 6 years of age
- Adults
- Patients who did not have any first-line stimulant treatment prior to their first prescription of Intuniv®

• Patients with prescribed overdose of >7 mg/day, or of >4 mg/day for patients ≤12 years of age

In this drug utilization study, patient medical record data will be collected within a prescriber survey. Annual study reports will be generated by IQVIA and sent to Shire in 2019, 2020, 2021 and 2022.

This protocol specifies the objectives of the study, describes the methodology and data sources, outlines the plans for statistical analysis, and details the tasks and timelines for the project.

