8.2 OBJECTIVES

Primary objectives:

- To characterize patients who are prescribed Intuniv® with a specific focus on
 - o Indications other than ADHD
 - o Children less than 6 years of age
 - o Adults
 - O Patients who did not have any first-line stimulant treatment prior to their first prescription of Intuniv®
 - o Prescribed overdose of >7 mg/day, or of >4 mg/day for patients ≤12 years of age
- To describe prescribing patterns of Intuniv® among physicians

Secondary objective:

• To measure the effectiveness of the additional risk minimisation measure (educational materials for healthcare professionals) in order to assess compliance with the indication and with visits and measurements needed during the first year of treatment

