9. RESEARCH METHODS

9.1 STUDY DESIGN

This is a multi-national, cross-sectional, non-interventional and anonymous web-based survey carried out among physicians. This approach was chosen as it will allow to collect all variables required, including data to assess compliance with the indication and with visits and measurements needed during the first year of treatment.

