9.7.3 Questionnaire analysis

The reports will include descriptive statistics of all parameters analyzed. As part of this analysis, the description of missing data for each outcome of interest will be provided. Missing values are expected to be few and distributed at random. Since there is no applicable method unanimously accepted, there will be no replacement or imputation of missing data (17).

For continuous variables the number of non-missing observations, mean, standard deviation, median, minimum and maximum will be presented.

Categorical data will be summarized using frequency and percentage. 95% confidence interval may be constructed around the percentage values for some variables. Some of the variables may also be summarized by country.

The educational materials will be considered to be effective if at least 80% of physicians will have responded correctly to at least 75% of the questions in the survey in which knowledge on the educational material is assessed.

This hypothesis is based on empirical numbers.

Evaluation of the success rate will be based on the percentage of correct answers to questions A2 to A5 in Section 4 ("Awareness and knowledge of risk minimisation measures") of the survey questionnaire.

Two analyses to evaluate the effectiveness of the risk minimization measures will be performed:

In the main analysis all questionnaires will be evaluated. In the subgroup analysis, only questionnaires of the physicians who answered "Yes" to question A7 ("Did you receive educational material regarding Intuniv[®]?") will be included. The subanalysis will allow to evaluate if awareness of the educational material may affect the number of correct answers.

More detailed information regarding the evaluation of the effectiveness is given in the survey SAP.

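### Section 9.7.3 concludes that the educational materials are effective from knowledge answers alone, although the secondary objective links effectiveness to compliance in practice

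*Protocol*

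**What the plan says.** The rule is in section 9.7.3: "The educational materials will be considered to be effective if at least 80% of physicians will have responded correctly to at least 75" (the 75 is a percentage of the questions that test knowledge of the materials). The success rate is "based on the percentage of correct answers to questions A2 to A5", which belong to the questionnaire section on awareness and knowledge. Two effectiveness analyses are planned. One uses all questionnaires, and the other uses only physicians who say they received the materials. Both count correct answers; of the second, the protocol says: "The subanalysis will allow to evaluate if awareness of the educational material may affect the number of correct answers".

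The objective is worded differently. Sections 4.3 and 8.2 set the secondary objective as measuring the effectiveness of the materials "in order to assess compliance with the indication and with visits and measurements needed during the first year of treatment". Section 9.1 justifies the web survey because it can supply every variable needed, "including data to assess compliance with the indication and with visits and measurements needed during the first year of treatment". Section 7 says the study is to evaluate whether the product "is being prescribed within the approved SmPC and whether current risk minimisation measures are adequate".

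Section 9.3 lists the patient-level variables that bear on this: diagnosis, age, earlier psychostimulant use, dose, monitoring visits in the first year, and weight, blood pressure and heart rate. Section 9.7.3 promises descriptive statistics for all of them and refers to the survey SAP for more detail on the effectiveness evaluation.

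**The concern.** The objective speaks of what physicians do, and the rule scores what they know. A physician can answer the monitoring questions correctly and still not see or measure patients as required. That gap is one of the things a study of risk minimisation should be able to show. As written, an annual report to the regulator could call the materials effective beside figures showing poor compliance, and the protocol gives no rule for reconciling the two.

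Section 9.9.2 adds a smaller worry. Online respondents may give socially expected answers or copy them from other sources, which would favour a knowledge score.

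**Working it through.** The protocol gives no calculation for the 80%/75% rule. Its only computed sizes (section 9.5.2) concern patient proportions: n = p(1−p)z²/e² with p = 0.5 and 95% confidence gives 384.15 for e = 0.05 and 96.04, rounded up to 97, for e = 0.10. These match the stated 384 and 97, but they do not bear on the rule. The check is therefore mainly a comparison of the sections.

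**Step 1. What enters the rule, and what the objective needs.**

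| Element of the secondary objective (8.2) | Collected (9.3)? | Described (9.7.3)? | In the effectiveness rule (9.7.3)? |
|---|---|---|---|
| Use according to the indication | Partly: diagnosis, age, prior psychostimulant | Yes | No |
| First-year visits | Yes | Yes | No |
| Measurements | Yes: weight, blood pressure, heart rate | Yes | No |
| Physician knowledge (A2 to A5) | Yes, in the questionnaire | Yes | Yes, the only input |

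**Step 2. The rule as a function.** Let K be the number of physicians, out of n, who answer at least 75% of A2 to A5 correctly. The materials are called effective if K/n ≥ 0.80. If A2 to A5 are four single questions (an assumption, as the questionnaire is not shown), a physician passes with 0.75 × 4 = 3 correct. Section 9.5.1 plans 15 to 20 physicians per country and year. If the rule is applied by country, the pass marks are 0.80 × 15 = 12 and 0.80 × 20 = 16.

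**Step 3. Probability of concluding effective.** With independent physicians and a true proportion π with adequate knowledge, this is P(K ≥ 0.80n) with K ~ Bin(n, π):

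| π | n = 15 (K ≥ 12) | n = 20 (K ≥ 16) |
|---|---|---|
| 0.70 | 0.30 | 0.24 |
| 0.80 | 0.65 | 0.63 |
| 0.90 | 0.94 | 0.96 |

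Compliance does not appear in the formula. Each entry is the same at any compliance level from 0% to 100%, given π.

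**Step 4. What the protocol calls the rule.** The amendment table (section 5) gives the reason for adding it: a process indicator of whether physicians' knowledge is adequate. The entry for Version 5.0 describes the percentage as the one for concluding effectiveness. The stated reason is narrower than the conclusion that section 9.7.3 attaches to the rule.

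**The case against.** The best case for the plan has five parts.

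- **The materials are meant to inform.** Section 7 says they were developed to raise awareness and knowledge of the monitoring requirements, so a knowledge test measures their immediate aim. This stands. It supports keeping the rule, but not the broader conclusion drawn from it, because section 8.2 goes beyond knowledge.
- **Poor practice would be visible.** A reader might infer that compliance is ignored and that the regulator would not learn of it. The documents do not support that. Non-ADHD use, age under 6, adult use, no prior stimulant and overdose are primary objectives. Visits and measurements are listed variables, all parameters are described, and the report goes to the EMA each year (section 12).
- **The objective is loosely worded.** A reader might infer that section 8.2 defines effectiveness as compliance. It does not: it links the two without giving a definition. The mismatch with section 9.7.3 remains.
- **The SAP may say more.** It was not available here and may contain compliance summaries. It cannot change the protocol sentence that fixes when the materials count as effective.
- **The bias argument applies to both kinds of data.** Section 9.9.2 also describes safeguards: no returning to earlier answers, and pre-populated items. The patient data come from the same physicians. The bias point is therefore only supporting.

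**Conclusion.** The point holds in a limited form. Compliance is left out of the effectiveness conclusion, not out of the study. Within that conclusion the omission is complete: no level of compliance can change it, and 12 of 15 or 16 of 20 physicians passing A2 to A5 decides it. Those counts assume that the rule is applied by country at the planned physician numbers. The three-of-four mark for each physician assumes four single questions. The main conclusion needs neither assumption, because it follows from the wording of sections 8.2 and 9.7.3.

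A reader might go further and require a fixed compliance threshold, such as the same 80%, with a double pass before the materials may be called effective. The documents give no basis for either. The study is declared descriptive, and there is no baseline from before the materials, so compliance levels alone could not be attributed to them.

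This should be fixed, because it changes what the study may conclude. It does not invalidate the data collection.

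**What to change.** In section 9.7.3:

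1. Call the 80%/75% rule a knowledge (process) indicator and limit its conclusion to adequate knowledge.
2. State that effectiveness under the secondary objective will be concluded only by interpreting this indicator together with patient-level proportions, each with a 95% confidence interval:
   - use outside the criteria already listed in section 8.2 (non-ADHD indication, age under 6, adults, no prior stimulant, overdose as defined there);
   - first-year visits, and weight, blood pressure and heart rate measurements, among patients with enough treatment time and available data.
3. Define the denominators in advance. The survey is cross-sectional, so patients treated for less than a year cannot show a complete first year, and section 4.6 collects monitoring data only where available.
4. Report absence of a prior stimulant as its own proportion, not as the complement of use within the indication. The label also covers patients for whom stimulants are unsuitable, and section 9.3 lists no variable for that.
5. Leave any numerical compliance threshold to the sponsor to justify.

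**Cost.** The change needs protocol and SAP wording and some derivation rules, with no new data. Intervals will be wide: at p = 0.5 the half-width is 1.96 × √(0.25/100) = 0.098 for 100 patients and 1.96 × √(0.25/50) = 0.139 for 50. Both treat patients as independent, although one physician may report up to ten, and the visit and measurement denominators will be smaller. A favourable overall conclusion becomes harder to reach. The compliance data remain physician-reported and without a baseline, which the report should state.

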9.8 QUALITY CONTROL

9.8.1 General considerations

The quality control for validating the results will be conducted at five levels:

- 1.) At the study level, all aspects of the DUS Intuniv[®], from scoping and protocol development to the reporting of the results will be conducted within the work-frame of IQVIA Quality Management System (QMS) and in accordance with the following policies and procedures:
 - POL_QA_001 "Quality Management System" policy
 - RWI_OP_PM0003 Post authorization safety studies (PASS)
 - RWI_OP_PM0004 Quality control of project deliverables
 - RWI_OP_PM0005 Quality control (QC) policy

According to the policies and procedures above, a Quality Control plan for the study will be developed and executed, which will include quality control on study methodology, statistical analysis plan, programming, data management and analysis, study results, conclusions and study report. Furthermore:

- The study Quality Control plan will establish ownership for the execution of the individual Quality Control steps. The principle of the independence of Quality Control applies.
- The Principal in charge of the study will ensure that individuals responsible for the execution of specific Quality Control steps will have knowledge, capability and experience which are adequate for the task.
- The result of the execution of the individual steps of the Quality Control plan will be documented, and include the required corrective actions, if any.
- The execution of any required corrective action will be documented.
- The executed Quality Control plan will be subjected to a final review and approval for sufficiency and completeness from the Principal in Charge of the study.

Also, the principal in charge of the study will verify training compliance of IQVIA employees contributing to the study, as per IQVIA procedure SOP_QA_007 "Training of Quality and Operational Standards".

- 2.) At IQVIA Medical Radar management level, every effort will be undertaken to collect complete and valid data:
 - Verification of the reliability and security of the web-questionnaire interface by a qualified web-master for each country,
 - Monitoring of the quality and datasets definition by a qualified data manager. In the background of the web-questionnaire, real-time checks of the answers provided by the respondents will be developed. Non admissible answers (i.e. incorrect or unusual values, outlying values) will be detected and queries sent to the physician.
- 3.) At the study database level (after merging datasets of each country), final data quality checks will be applied (beyond data management process):
 - Distribution of each variable in order to count the number of missing values and estimate the associated relative percentage,
 - Identification and count of non-analyzable questionnaires:

• Estimation of the percentage of physicians without complete analysable questionnaire.

Any changes in the database will be tracked and documented. The country-datasets will be stored in a dedicated database. After data have been validated and quality checked, the database will be locked.

- 4.) At the statistical analysis level: all data management and statistical analysis programs developed and used in the analysis will be documented. All versions generated will be dated, kept with accompanying documentation and archived. The original database will be stored. A derived database will be created for the new versions of the data in order to include recoding and computing of new variables, especially stratification of continuous variables, combination of modalities for categorical variables, calculation of composite indicators, etc.
- 5.) At the results level, a data review will be done to ensure data integrity.

9.8.2 Approaches for validating the questionnaire

The questionnaire will be tested among 5-6 physicians for its comprehensibility, consistency and the appropriateness of medical terms. The questionnaire will be translated into local languages using the back and forth method (translation from English to local language, then again to English) to ensure correct translation and that appropriate wording is used.

9.8.3 Safeguards, security and traceability of calls

The operators of the call centre specialized in health surveys, will be assigned to the project and trained on the survey methodology prior to fieldwork. The phone calls will be traced using the call management software. All survey aspects from protocol development to the reporting of the results will be conducted according to the SOPs of IQVIA and IQVIA Medical Radar divisions.

9.9 LIMITATIONS OF THE RESEARCH METHODS

9.9.1 Possible selection bias due to voluntary participation

The selection bias of physicians participating in a survey is an inherent bias to any study based on volunteer participation. In order to quantify any selection bias, the distribution of each stratification criterion of healthcare professional (country and specialty) will be compared between participants and non-participants.

9.9.2 Limits inherent to web-surveys

The questionnaire includes general questions followed by specific ones. As the physicians may understand the right answer in subsequent questions, it would not be possible to go back in the questionnaire and edit answers in former questions.

In such surveys, the generalisation and external validity of the results is restricted to physicians who have an active email address and willing (and able) to answer a

questionnaire online. These physicians may not be fully representative of the whole targeted population (18).

Among non-response bias, targeted physicians may also have activated filters in their mailbox in order to block spams and unsolicited emails. They may not even see the invitation to participate in the survey if a very strict degree of message filtering is set. Having multiple email addresses could also be a critical situation. If the one used is not the primary address, or if the physicians do not check their email box frequently, they will not receive the invitation during the recruitment period. This is one of the reasons why the physicians will also be contacted by phone.

Moreover, web-surveys may promote social desirability bias which refers to the tendency of physicians to give socially desirable/expected responses instead of choosing those reflecting their current knowledge or behavior, e.g. physicians can copy-paste information collected online instead of giving their own opinions (18).

Social desirability can affect the validity of survey research findings, but the use of prepopulated items in the questionnaire could/tends to reduce this bias (19).

The access to the web-questionnaire interface will be strictly limited to the invited participants, with the possibility to participate only once and a traceability system. Thus stakeholder bias (multiple answers of people who have a personal interest in survey results and/or who incite peers to fulfill the survey in order to influence the results) or unverified respondents (when it is not possible to verify who responds) are not applicable.

9.10 OTHER ASPECTS

None

10. PROTECTION OF HUMAN SUBJECTS

The survey is non-interventional and totally anonymous to the study sponsor. Data collected will remain absolutely confidential, and only aggregated data will be analysed and communicated in a report.

10.1 REGULATORY AND ETHICS CONSIDERATIONS

10.1.1 Ethical principles, laws and regulations

The survey will follow the regulatory and ethical requirements of each country. IQVIA will follow the European Pharmaceutical Marketing Research Association (EphMRA) guidelines (20) for all participating countries, and specific local requirements will be applied. The study is not intended to influence the physicians' prescribing behavior by any means. Rather, it seeks to measure knowledge and prescribing behaviors of the physicians as closely as possible to real life practice.

10.2 PHYSICIANS INFORMATION

Physicians participating in the survey will be informed about targets of the investigation, the nature of the transmitted data, the intended use of data, recipients of these data, and

their right of access and rectification to their personal data, as well as their right of objection to use their data or to IQVIA keeping their data.

10.2.1 Physicians compensations

Physicians will be offered a compensation for the time spent participating in this survey (which they may refuse). The time to complete the survey is estimated to be between 5 to 10 minutes, plus an additional 10 minutes for each patient questionnaire.

The amount of this compensation will be determined according to the EphMRA recommendations and the Association of Opinion and Behaviour in health field research companies (ASOCS) charter, and which states:

"When it is necessary to compensate a physician in return to the time spent during an interview or a group meeting, the compensation must not exceed the fees commonly taken by the physician for his/her advice or consultation and must be proportional to the time provided. The compensations should be clearly stated prior to the physician's participation in the survey. They must be declared to the tax authorities in accordance with applicable laws".

10.3 CONFIDENTIALITY

10.3.1 Patient confidentiality

The survey is non-interventional and totally anonymous to the study sponsor. Data collected will remain absolutely confidential, and only aggregated data will be communicated and analysed.

10.3.2 Data confidentiality / Data security

The answers provided by the physicians will be collected in an anonymous way. Only aggregated data and presented as a synthesis will be transmitted to the MAHs.

Participating physicians will access the website (https secured site) using a personalised login and their password.

Data will be recorded in a central database and tracked using an audit trail. The system will enable retrieving all introduced data at any time, and will include security elements to prevent others than authorized staff from accessing data. Each user will have a specific profile which will limit his/her use of the database. A security copy of the database and the application files will be made outside the server housing the web-based study. Security copies will be periodically made and stored outside this server. A copy of the data stored in the database will be transferred to MAHs at the end of the study.

Description of all elements of security and traceability will be available upon request.

